9.4. Final Study Visit (Visit 4)

1. Study staff will verify the patient by the name on the record;
2. Study staff will administer the **Visit 4 Quantitative Assessment**.
3. Study staff will assess **self-reported adherence**, measure weight, and assess pregnancy status (women only).

4. Study staff will obtain **blood samples for the following assessments**: DBS and VL (see Blood Specimen SOP for additional details).
5. Study staff will check in with the participant regarding any time(s) participant took a dose without using Wisepill, and collect used Wisepill.
6. Study staff will update ARV regimen and dosing time(s).
7. Study staff will give the participant **compensation**.

9.5. Clinic Chart Review (Visits 1-4 and Post Study)

Study staff will review participants' clinic charts at all visits and post-study to determine if any changes to medical or adherence management were made by providers since the previous visit. These changes could include: additional VL requests (beyond those prescribed for a stable patient), referral for intensive counsellor-based or group adherence counselling (usually only accessed if VL flagged as raised), outreach by Community Care Workers (CCWs) for adherence monitoring and support; and additional doctor-requested patient appointments. To mitigate the risk of control group participants receiving interventional DBS feedback, providers will not receive DBS results for participants in the control group.

The expected quality of the notes in the clinical charts will be variable with some clinicians making detailed notes and others making less detailed notes. The study team is reviewing FDW feedback and considering the creation of a checklist to facilitate identifying and quantifying actions that a provider may take based on DBS results .

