8.1 Inclusion/Exclusion Criteria

8.1.1. Patient Participant Inclusion Criteria

Individuals who meet all of the following criteria are eligible for inclusion in the study:

- 18 years of age or older
- HIV-positive
- Initiated ARV's containing tenofovir 4 or more months ago

- Speaks English or Xhosa
- Willing to attend 5 study visits approximately one month apart
- Willing to allow the study team to contact his/her HIV care provider about his/her monthly TFV-DP drug level
- Willing to use Wisepill to dispense ARVs for 4 months
- Willing to receive SMS and/or phone call reminders to charge the Wisepill
- Willing to allow the study team access to their medical chart/clinic folder

Participants will be recruited without regard to gender or race/ethnicity. However, based on clinic profiles, we expect the majority (about 70%) to be women and over 90% to be Black African, with the remainder, if any, of mixed race.

To generate a study sample that closely represents the clinic population, participants will be recruited regardless of VL. Based on clinic profiles, we expect the majority of participants (about 80%) to be virally suppressed based on the last standard of care (SoC) VL with the remainder being unsuppressed. The South African National Health Laboratory Service (N HLS), which assays the VL, currently uses a cut-off of less than 50 copies/mL to denote undetectable VL.

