8.4 Screening for Eligibility

After the patient gives permission to review her/his medical/research records, the study staff member will screen for eligibility by examining the medical records to confirm that the patient initiated ART containing tenofovir within the last 4 months and record the most recent VL value and date of draw.

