14.3 Informed Consent

14.3.1 Informed consent process.

Informed consent will be obtained from each study participant prior to conducting study-related procedures. The informed consent process will be conducted by study staff in Xhosa or English, at the preference of the participant, and the consent form will be available in both languages. Participants will be told that participation in this study is completely voluntary and their decision whether or not to participate in the study will not affect any medical treatment they are receiving at the clinic or their participation in any other studies being conducted by the DTHF. All study procedures will be described and they will be told that all information will be kept confidential within the limits of the law.

There will also be optional activities that are not required in order to participate which include:

- The disclosure of DBS results to a patient's provider if they were in the control group
- The possibility for study staff to conduct a home visit if the patients misses a study visit.
- Participation in future study visits

Once the study has been explained in detail, time will be given for participant questions. If the participant wants to join the study, she/he will provide informed consent by signing the informed

consent form, or for those who are cannot write, by providing a fingerprint. (Further details regarding DAIDS requirements for documenting the informed consent process are provided in the DAIDS Standard Operating Procedure for Source Documentation.) A copy will be given to the participant to take home and a signed copy will be stored securely in a locked file cabinet in a locked room.

14.3.2 Assent process.

Not applicable.

14.3.3 Documentation of informed consent.

Participants will document their provision of informed consent by signing the informed consent forms. The presence of a witness, use of a translator, and which language was used to obtain the informed consent form will be documented in the informed consent source document.

14.3.4 Waiver of informed consent.

Not applicable.

14.3.5 Waiver of documentation of informed consent.

Not applicable.

14.3.6 Stored samples and associated data considerations.

All blood samples will only be labeled with the participant's study identification number and the date of collection (no identifying information will be included).

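### Additional VL requests are judged against a stable patient although about 12 of 60 participants are expected to enrol unsuppressed, so routine care dilutes the provider comparison; the checklist worded around DBS results should be made arm-neutral

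*Combined protocol and SAP*

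**What the plan says.** - **What counts as a change (9.5).** Staff review charts at every follow-up visit and post-study for changes since the previous visit. The examples include "additional VL requests (beyond those prescribed for a stable patient" and "referral for intensive counsellor-based or group adherence counselling (usually only accessed if VL flagged as raised". Outreach by community care workers and extra doctor-requested appointments are also listed, without a benchmark. Section 12.1 carries the same raised-VL premise into the provider analysis, and gives no model, counting rule or effect size for it.
- **Who is enrolled (8.1.1).** Recruitment is regardless of VL, and "we expect the majority of participants (about 80%) to be virally suppressed" on their last standard-of-care result, with the remainder unsuppressed. The Aim 1 cohort, by contrast, was suppressed at enrolment (5.1.4).
- **What is known at entry (8.4).** Screening staff "record the most recent VL value and date of draw". No stratification by VL appears in 12.4, and no VL adjustment is given for provider actions.
- **The checklist (9.5).** The team is "considering the creation of a checklist to facilitate identifying and quantifying actions that a provider may take based on DBS results". The same section expects chart notes to vary in detail and says that "providers will not receive DBS results for participants in the control group".
- **Masking.** Section 12.4 says the study is not blinded. The baseline assessor is to be blind to arm (9.7.1), but nothing similar is said of chart reviewers.
- **Optional consent (14.3.1).** The optional items include "The disclosure of DBS results to a patient's provider if they were in the control group". No timing is given.

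**The concern.** A stable-patient benchmark suits a suppressed cohort. In a participant whose last VL was raised, a repeat VL or a counselling referral may be the clinic's ordinary response. The protocol itself describes a raised VL as the usual trigger for such counselling. Under 9.5 these actions are recorded as management changes even when drug-level feedback had nothing to do with them. Clinical management is named in primary objective (b) (6.1). In a comparison of 30 against 30, such background actions make a feedback effect harder to see, and an uneven split of unsuppressed participants moves the difference in either direction.

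The checklist raises a different problem. If its items are tied to DBS results, it has nothing to capture in a control chart, where the provider has no such result. Control-arm actions would then be found only through free-text notes of variable detail. That would be bias, and it would favour Feedback.

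**Working it through.** **The plan's own figures.** None is given for provider actions. The detectable difference of 5.59 points in 12.1 concerns patient adherence. A standard formula gives 2.8016 × 11.42 × √[(2/30) × 1.4/3] = 5.64, close to the stated value, and it has no bearing on this point.

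**Expected number unsuppressed.** (100% − 80%) × 60 = 12, about 6 per arm.

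**Chance imbalance.** With 30:30 allocation and no stratification, let X be the number of the 12 allocated to Feedback. X is hypergeometric: P(X = x) = C(12, x) C(48, 30 − x) / C(60, 30).

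| Split | Towards Feedback | Either direction |
|---|---|---|
| 8:4 or worse | 0.17 | 0.33 |
| 9:3 or worse | 0.05 | 0.10 |

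**Dilution (assumed rates; the documents give none).** Suppose 5% of suppressed participants have some counted action anyway, a share r of unsuppressed participants have a routine one, and feedback adds an action in 30% of those without one. The control rate is c = 0.2r + 0.8 × 0.05 and the Feedback rate is t = c + 0.30(1 − c). Power is Φ[(t − c − 1.96·se₀)/se₁], with se₀ from the pooled rate and se₁ from the separate rates, 30 per arm, two-sided 5%.

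For r = 50%: c = 0.14, t = 0.14 + 0.30 × 0.86 = 0.398 and t − c = 0.258. Then se₀ = √(0.269 × 0.731 × 2/30) = 0.1145 and se₁ = √[(0.398 × 0.602 + 0.14 × 0.86)/30] = 0.1095. Power is Φ[(0.258 − 1.96 × 0.1145)/0.1095] = 0.62.

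| r | c | t | Power, any action |
|---|---|---|---|
| 25% | 0.09 | 0.363 | 0.73 |
| 50% | 0.14 | 0.398 | 0.62 |
| 75% | 0.19 | 0.433 | 0.53 |
| 100% | 0.24 | 0.468 | 0.45 |

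For reference, the 24 suppressed participants per arm alone give 0.72 whatever r is. The loss is negligible at r = 25% and substantial only if most unsuppressed participants have a routine action within follow-up.

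**Checklist (assumed rates).** Take the same true action rate in both arms, 90% capture in Feedback and 90%, 60%, 30% or 0% in Control. At a true rate of 30% and capture of 90% against 30%, the spurious difference is 0.30 × (0.90 − 0.30) = 18 points. Rejection rates are for a two-sided 5% Fisher exact test, 30 per arm.

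| Control capture | Spurious difference (true rate 30%) | False-positive rate, true rate 30% | False-positive rate, true rate 10% |
|---|---|---|---|
| 90% | 0 points | 0.03 | 0.01 |
| 60% | 9 points | 0.08 | 0.01 |
| 30% | 18 points | 0.31 | 0.02 |
| 0% | 27 points | 0.86 | 0.05 |

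The bias can be material, but only if the checklist works in one arm only and actions are fairly common.

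**The case against.** The best defence is that the plan already treats the arms alike. Section 4 promises monitoring in both groups, 9.5 sets no arm limit on chart review, and Table 1 restricts the feedback row to one arm but not the chart-review row. Routine care falls in both randomised arms. The checklist is undecided, and its wording can be read as a list of action types that fits any chart. All of this stands, and it rules out several stronger readings:

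- **That provider actions are being ascertained unequally.** The text describes a risk in a tool not yet adopted, not a planned inequality.
- **That counting routine care biases the result towards feedback.** It adds noise. Even if all 12 unsuppressed participants and nobody else had an action, an 8:4 split gives 8/30 against 4/30, Fisher p = 0.33.
- **That every provider action is scored against a stable patient.** That benchmark is attached to VL requests only. The counselling item carries a parallel raised-VL premise, and the other two examples carry none.
- **That controls have no DBS results.** DBS is collected from everyone at every visit (9.9.1.1). What is withheld is reporting to control-arm providers.

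Two further points limit the size. Changes are counted since the previous visit, so a response completed before enrolment is not a new change, and routine VL is typically annual (5.1.2), so the last result may be old. Against this, some participants are approached straight after a routine VL draw (8.2.2), with baseline within 2 weeks (8.5), so a clinic response can still fall within follow-up. Finally, chart counts are not among the measures listed for the primary endpoint in 12.2.1, and the work is a pilot. They do serve objective (b), which names clinical management.

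A tempting remedy is to count only actions with no preceding raised VL. That conditions on a post-randomisation event: if feedback prompts an extra VL, the VL is raised and counselling follows, the counselling would be discarded although feedback led to it.

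**Conclusion.** The concern holds in limited form. For about 12 of 60 participants the stable-patient benchmark for VL requests does not fit, and the raised-VL counselling item has the same weakness. Routine care is therefore counted as provider change in both arms. The consequences are dilution and chance imbalance: an 8:4 or worse split has probability 0.33 in either direction and 0.17 towards Feedback. In the assumed illustration, power runs from 0.73 down to 0.45 as the routine-action rate in unsuppressed participants goes from 25% to 100%. A reader might infer systematic bias from this part, but randomisation with the same chart review in both arms does not support that.

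The checklist is a conditional risk. It would become bias only if items tied to DBS results were applied literally, and the plan does not say that they will be. The imbalance figures rest on the plan's 80% and on 30:30 allocation without stratification. The power and capture figures rest on assumed rates. The changes are worth making now because the checklist is still being designed.

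**What to change.** 1. In 9.5, define an additional VL request against what standard of care already calls for given the participant's VL status at screening.
2. Keep all provider actions as the main count. Compare arms stratified by or adjusted for the screening VL status recorded under 8.4, stating the cut-off in advance.
3. For each action, record its date and whether a raised standard-of-care VL preceded it. Use this for description only, never to remove actions from the count.
4. Make any checklist a single arm-neutral form with identical items, completed for all 60 charts whether or not a DBS result is mentioned. Mask the abstractor to arm where practicable.
5. Reconcile the optional disclosure of control-arm DBS results in 14.3.1 with the statement in 9.5 that control-arm providers do not receive them, including when any disclosure would occur.

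The cost is two extra fields on the abstraction form and one stratified table. The limitation is that unsuppressed strata of about 6 per arm will be imprecise and cannot support conclusions of their own.

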9.6. Provider Focus Group Discussions

Once all pilot participants have completed their final visit (visit 4), study staff will hold the provider FGD to ascertain their understanding and perception of the utility of the DBS feedback and what changes they made (if any) in managing the participant's care and what additional communication (if any) they initiated with the participant. Closer to the end of the Aim 2 study, a focus group guide will be developed prompting providers to comment on whether the initial training prepared them to provide these results, whether they needed additional training, experiences they had during the study trial, and to describe any other thoughts or opinions that could inform feasibility and future scale-up of DBS feedback efforts in clinical settings. As this FGD might be scheduled out a month or two following the end of the study trial, providers will be given a window of 6-8 months for study participation.

9.7. Assessments

Detailed information about the following assessments can be found in the [Assessment SOP](#).

9.7.1. Baseline Quantitative Assessments

At Visit 0, an RA will conduct the Baseline Quantitative Assessment, entering responses on an electronic tablet. The Baseline Quantitative Assessment will address the following domains associated with adherence and study participation with measures that have been used successfully in SA research, including our own prior studies. The Baseline Quantitative

Assessment will take approximately 1½ hours to complete. The RA conducting assessments will be blind to participant's study condition.

Socio-demographic characteristics will include gender; age; education; income and employment status; household composition; dwelling type; access to running water, electricity, and toilet; and missed meals in last month.

Medical history, assessed from the patient, will include time since HIV diagnosis, time on ART, type of ARV medication, last CD4+ cell count, last VL result, and comorbid conditions (e.g., TB, anemia), height and weight.

Social support, medication beliefs, and other contextual factors will include life events, patient-clinic relationship, medication social support, HIV stigma, HIV treatment knowledge, beliefs about medication and HIV, HIV disclosure, mental health, and substance use.

9.7.2 Visit 4 Quantitative Assessments

The Visit 4 Quantitative Assessment is a reduced version of the Baseline Quantitative Assessment. It will include a briefer battery of socio-demographic, medical history, social support or medication beliefs assessments. It will more focus on mental health, substance use, medication social support and life events. The Visit 4 Quantitative Assessment will encompass the Exit Interview and will take approximately 1 hour to complete.

9.7.3. Exit interview

Study staff will administer a semi-structured Exit Interview during the Visit 4 Quantitative Assessment to all study participants. Feedback arm participants will be asked about their understanding and perceptions of the meaning of the drug-level feedback, whether (and if so how) the feedback from the study staff and/or providers influence participants' behavior (e.g., medication-taking, disclosure to people in their social network, seeking adherence support, etc.). No feedback arm participants will be asked about if/how they would like to receive feedback if this was put into routine clinical practice (e.g., from a lay HCW, from a doctor, by SMS).

In both cases, the Exit Interview assessment will include closed and open-ended questions exploring the patient's thoughts about receiving DBS-based feedback.

9.7.4. Self-Reported Adherence Questionnaire.

Study staff will assess self-reported adherence in the past 30 days at every visit. The Self-Reported Adherence Questionnaire will take approximately 3 minutes to complete.

9.7.5. Pregnancy Status.

At each study visit, study staff will ask study participants (women only) whether they are currently pregnant or plan to become pregnant.

9.8. Wisepill

We will continuously monitor Wisepill (Wisepill Technologies, SA) device openings. This electronic monitoring device is a pill box that sends a signal to a secure website via cellular data

networks whenever the device is opened as a proxy for ART adherence. If connection or SIM card problems prevent real-time monitoring, records and diagnostics are stored (up to 1 year) and uploaded to the server when a connection is re-established. The device can store up to a 30-day supply of medication depending on number/size of pills. Since the majority of our participants will be on single-pill, single daily dose ARV regimens, the device will hold a 30-day supply. Wisepill-measured adherence will be operationalized as percentage of days/doses for which a device-opening signal was received in the past month.

9.8.1 Wisepill distribution and instruction.

At the baseline visit, study staff will give the participant a Wisepill device and instruct her/him on how to fill the device, open it for dosing, and re-charge the battery. Before ending this session, study staff will confirm that the Wisepill device is properly set up, that it is recognized by the Wisepill server, and that device openings are being recorded properly (date and time). Participants will be asked to bring the device with them to all study visits. Participants will also be informed that when a participants' device battery gets low, the server will automatically send an SMS to the participant reminding them to charge the device; if 7-days pass after the SMS reminder and the device still appears with a low or flat battery or is not seen at all on the server, study staff will call the participant to remind her/him to charge the battery.

At each subsequent study visit, study staff will ask if the participant is having any problems using Wisepill and will remind her/him to charge the device at least once per month and/or when the red light is blinking. If necessary, devices can be charged in the clinic or the current Wisepill battery can be replaced. Study staff will also conduct a Wisepill test to confirm that the device is properly connecting to the data server. Lastly, study staff will ask participants if her/his ARV medication or dosing schedule has changed since the previous visit and will update this information as necessary. Participants will use the Wisepill Device for four months.

Wisepill is being used in this study for measurement purposes, and not for clinical intervention purposes. As Wisepill information has not been sufficiently validated for clinical use, Wisepill information will not be shared with participants or providers involved in this study.

9.9. Blood Specimens

9.9.1. Blood specimen preparation, handling and shipping

Study staff will obtain the following blood samples: DBS, VL, and hematocrit (only at Baseline). In all cases, blood collection will be performed by trained study staff using sterile technique.

9.9.1.1. DBS samples for TFV-DP assay

DBS samples will be collected at every study visit by spotting blood directly into each of the five circles on a Whatman 903 ProteinSaver card (see Blood Specimen SOP for additional details). Study staff will take care to ensure that both hands are gloved before handling the DBS card, to not touch the areas where the blood spots will be placed with either her/his own or the participant's finger(s), to obtain spots of sufficient diameter, and to not over-run the circle markings. Study staff will ensure that DBS cards are labeled with the participant ID, visit number, and air-dried for 3 hours, individually packaged in a plastic bag with a desiccant pack and a humidity indicator card, and transferred to a -20°C freezer for short-term storage at the GRO. DBS cards will be transferred

at least twice a week to the Groote Schuur CRS for longer term storage at -80°C until transfer to the UCT Clinical Pharmacology laboratory for assay.

At the Clinical Pharmacology laboratory a 3mm disc will be punched from the DBS and extracted with 500µl of 70:30 methanol-H₂O with sonication. Supernatants will be stored at -80°C until they are assayed by LC-MS/MS using [name]'s validated assay for TFV-DP. We will use modeling to assess sources of variability in this study and will also consider other factors that could interfere with drug levels other than adherence alone, including comorbid conditions captured by the Medical History obtained at Baseline and Visit 4. We do not anticipate that the use of concomitant nephrotoxic medications will have an effect on these drug levels while the renal function is preserved.

